4.1. Eligibility

Screening for eligible participants will be performed within 8 weeks before the first administration of study vaccine at Week 0. Study participants must be healthy (on the basis of medical history, physical examination, vital signs measurement, and laboratory assessments), adult men and women, aged 18 to 50 years.

4.1.1. Inclusion Criteria

A volunteer must meet all of the following criteria:

1. 18 to 50 years old
2. Available for clinical follow-up through Week 48 after enrollment
3. Able to provide proof of identity to the satisfaction of the study clinician completing the enrollment process. Proof of identity includes a valid U.S. government-issued or state-issued photo ID such as a driver's license, military ID, or U.S. passport.
4. Able and willing to provide a personal mobile phone number or home phone number at which the participant can be reliably contacted. Participants will be contacted primarily for study visit 2A (Appendix 1), as a reminder of an upcoming visit, and after missed visits for rescheduling purposes.
5. Able and willing to complete the informed consent process and demonstrate understanding with a passing score (90% or greater) on the Assessment of Understanding (AOU) by the third attempt.

6. In good general health without clinically significant medical history.
7. Physical examination and laboratory results without clinically significant findings and a body mass index (BMI) ≤ 40 within the 56 days prior to enrollment.

Laboratory Criteria within 56 days prior to enrollment:

8. Hemoglobin ≥ 11.5 g/dL for women; ≥ 13.0 g/dL for men.
9. White blood cells (WBC) = 3,300-12,000 cells/mm³.
10. Total lymphocyte count ≥ 800 cells/mm³.
11. Platelets = 125,000 – 400,000/mm³.
12. Alanine aminotransferase (ALT) ≤ 1.25 x upper limit of normal.
13. Serum creatinine ≤ 1 x upper limit of normal.
14. HIV-uninfected as evidenced by a negative FDA-approved HIV diagnostic blood test.

Female-Specific Criteria:

15. Negative β -HCG (human chorionic gonadotropin) pregnancy test; serum β -HCG at screening (or urine if screening is the same day as enrollment) and urine β -HCG at enrollment if woman is of reproductive potential.
16. Agrees to use an effective means of birth control from at least 21 days prior to enrollment through 24 weeks after study vaccination if assessed to be of reproductive potential.

4.1.2. Exclusion Criteria

A volunteer will be excluded if one or more of the following conditions apply:

Volunteer has received any of the following substances:

1. Investigational Ebola or Marburg vaccine in a prior clinical trial or prior receipt of a cAd3 adenoviral vectored investigational vaccine.
2. Immunosuppressive medications within 2 weeks prior to enrollment.
3. Blood products within 112 days (16 weeks) prior to enrollment.
4. Investigational research agents within 28 days (4 weeks) prior to enrollment.
5. Live attenuated vaccines within 28 days (4 weeks) prior to enrollment.
6. Subunit or killed vaccines within 14 days (2 weeks) prior to enrollment.
7. Current anti-tuberculosis prophylaxis or therapy.

Female-specific criteria:

8. Woman who is pregnant, breast-feeding or planning to become pregnant during the first 24 weeks after study vaccine administration.

Volunteer has a history of any of the following clinically significant conditions:

9. Serious adverse reactions to vaccines such as anaphylaxis, urticaria (hives), respiratory difficulty, angioedema, or abdominal pain.
10. Allergic reaction to excipients in the study vaccine including gentamycin, neomycin or streptomycin.
11. Clinically significant autoimmune disease or immunodeficiency.
12. Asthma that is not well controlled.
13. Positive syphilis serology. False-positive results will also exclude a participant.
14. Diabetes mellitus (type I or II).
15. Thyroid disease that is not well controlled.
16. A history of hereditary angioedema (HAE), acquired angioedema (AAE), or idiopathic forms of angioedema.
17. Idiopathic urticaria within the last 1 year.
18. Hypertension that is not well controlled.
19. Bleeding disorder diagnosed by a doctor (e.g. factor deficiency, coagulopathy, or platelet disorder requiring special precautions) or significant bruising or bleeding difficulties with IM injections or blood draws.
20. A malignancy that is active, currently being treated, or not surgically cured.
21. Seizure in the past 3 years or treatment for seizure disorder in the past 3 years.
22. Asplenia or functional asplenia.
23. Psychiatric condition that precludes compliance with the protocol; past or present psychoses; or within five years prior to enrollment, history of a suicide plan or attempt.
24. Any medical, psychiatric, social condition, occupational reason or other responsibility that, in the judgment of the investigator, is a contraindication to protocol participation or impairs a volunteer's ability to give informed consent.

5.0 STUDY PROCEDURES

5.1. Schedule of Evaluations

Evaluation of the safety of this vaccine will include laboratory studies, medical history, physical assessment by clinicians, and participant self-assessment recorded on a 7-day diary card. The schedule of study visits, permitted windows for completing the visits, and evaluations performed at each visit are shown in Appendix 1. Total blood volume drawn from each participant will not exceed 550 mL in any 8-week period.

5.1.1. Recruitment

Healthy adult participants, male and female, military and civilian, will be recruited by non-coercive means through the WRAIR CTC. Participants will be recruited from the Baltimore-Washington, D.C. area through the WRAIR CTC according to applicable U.S. Army regulations (i.e., 32 CFR 219 and 21 CFR 50, 54, 56, and 312). Participants will be recruited by the use of WRAIR IRB approved advertisements such as newspaper advertisements, flyers, posters, generic radio advertisements, social media posts, and word of mouth and referrals from participants currently in studies. All recruitment materials will have been reviewed and approved by the WRAIR IRB prior to their use. All recruiting methods will direct the participant to contact the CTC via e-mail or phone, or to the CTC web site where the same contact information will be given.

Participants can also be recruited via WRAIR 2038, which is a generic screening protocol managed by the WRAIR CTC. Under this screening protocol, participants will undergo a generic screening visit with medical history, exam, vitals, lab tests, along with other potential screening tests.

If the participant is interested in learning about this clinical trial, they will need to attend a briefing and sign this study's informed consent form. If the participant consents, the screening documentation from WRAIR 2038 can be shared with this study to fulfill screening requirements, and a copy of said documents can be added to the participant's study file for this clinical trial.

5.1.2. Consent Procedures and Screening

Following the briefing sessions, volunteers who remain interested in the study will be scheduled for a screening visit. At the beginning of the screening visit, written informed consent will be obtained from the volunteer by the PI or their designee. Written informed consent will be obtained from each participant before any study procedures are performed. All informed consent forms will be administered individually, in a private setting, with strict respect of confidentiality. Participants will be given ample time and opportunity to inquire about details of the study, discuss with close family members or friends and ask any questions before dating and signing the consent forms. A copy of the signed informed consent form will be given to the participant along with a copy of the volunteer event schedule (Appendix 5). The consenting process will be documented in the case report forms (CRFs).

After providing signed informed consent the volunteer will complete an AOU. Volunteers are allowed to take the AOU three times, but must have a passing score (90% or greater) by the third attempt to participate in the study. If after 3 attempts to pass the AOU the volunteer is unable to do so, the volunteer will become ineligible for study participation. Volunteers who successfully pass the AOU will then be screened as per the study protocol.

Volunteers who have passed the AOU and have given written informed consent will undergo a complete medical history, physical examination, and screening laboratory assessments to determine eligibility for trial participation. The following screening assessments will be completed after the informed consent process has been completed:

- Medical history
- Physical exam
- Vital signs and weight
- Serum (or urine if screening is the same day enrollment) pregnancy test for all females
- CBC with total lymphocyte count
- Creatinine
- ALT
- HIV testing (including pre/post-test counseling)
- Syphilis testing
- Pre-existing vector immunity testing
- Serum storage for antibody assays
- Peripheral blood mononuclear cells (PBMC) and plasma for storage

Screening evaluations for specific eligibility criteria (see Sections 4.1.1 and 4.1.2) must be completed within the screening visit window specified (Appendix 1) prior to enrollment, but may be repeated, if the initial laboratory result is not deemed medically significant, within the screening visit window in order to confirm eligibility. Samples for storage may also be collected within the screening visit window. Counseling on the potential risks of becoming pregnant during study participation will be provided. Pre-HIV test counseling and post-HIV test counseling will be provided during the screening process.

Study volunteers may be scheduled for a second Screening Visit to evaluate laboratory and test results if an abnormality or illness had been identified at the first screening. This approach will allow study staff to evaluate the recovery from any illness identified at the first screening as well as to repeat screening laboratory tests that were abnormal at the first screen due to transient illness.

Eligible and willing volunteers will be scheduled for an appointment for enrollment and the initial vaccination visit within 56 days of having satisfied eligibility requirements.

5.1.3. Day 0 Through Week 48

Day 0 is defined as the day of protocol enrollment and the study injection. Study eligibility criteria are reviewed on Day 0 as part of the enrollment process. If clinical assessment on Day 0 suggests significant changes may have occurred since the screening visit, then the physical examination, hematology tests, blood chemistries, and urinalysis done at screening must be repeated, as appropriate, before the participant receives the experimental vaccine. Pregnancy test results for women of childbearing potential must be obtained prior to the study injection. Day 0 evaluations immediately prior to the first injection are the baseline for subsequent safety assessments.

Refer to the table in Appendix 1 for details on the SOE and the window(s) permitted. After Day 0, deviations from the visit windows in completing study visits are discouraged and will be recorded as protocol deviations, but are permitted, at the discretion of the PI (or designee), in

consultation with the sponsor, in the interest of obtaining participant safety and immunogenicity evaluations following exposure to the investigational vaccine.

Study visit procedures and tests through Week 48 include the following as indicated in the SOE (Appendix 1):

1. Signature of study participation informed consent form
2. AOU (prior to enrollment)
3. Clinical evaluations: vital signs; targeted physical examination on any visit if indicated by interim complaints or laboratory findings
4. Interim medical history, including any new medications taken
5. Counseling on avoidance of pregnancy
6. Post-injection vital signs and assessment of injection site at 30 or 60 minutes post-injection (60 minutes for first 3 participants of each group and a minimum of 30 minutes for subsequent participants in each group).
7. Diary Card: Baseline in the evening on the day of injection; 7-day diary card for self-assessment by participant
8. Urine pregnancy test for females of reproductive potential
9. CBC, total lymphocyte count, platelet counts
10. Blood creatinine and ALT
11. HLA Type
12. Serum, PBMCs, and plasma for protocol assessments and archiving
13. Intracellular RNA

At intervals specified in the SOE, blood will be drawn for safety and immunologic assays. Total blood volume drawn from each participant will not exceed 550 mL in any 8-week period. Research blood samples will be processed and stored at VIP.

Stored samples with consent for genetic testing may be used to elucidate genetic factors associated with immune response to a vaccine and to further evaluate responses to the vaccine. Results from genetic testing will not be provided to participants as the results not are validated for clinical use. Any remnant cells, serum, or plasma will be stored for future exploratory virological and immunological assays as per individual participant's consent for future use.

5.2. Administration of the Study Injection

Injections will be administered IM in a 1 mL volume by needle and syringe. It is recommended, but not required, that the injection be administered into the non-dominant arm. When choosing an arm for the injection, clinicians should consider if there is an arm injury, local skin problem or significant tattoo that precludes administering the injection or will interfere with evaluating the arm after injection. Procedures for follow-up in the clinic after vaccination are shown in Appendix 1.

Following the study injection, participants will be observed in the WRAIR CTC for a minimum of 30 or 60 minutes (60 minutes for first 3 participants of each group and a minimum of 30 minutes for subsequent participants in each group). Vital signs (temperature, blood pressure, and pulse) will be taken 30 or 60 minutes post-injection. The injection site will be inspected for evidence of local reaction during this period. In keeping with good medical practice, acute medical care will be provided to participants for any immediate allergic reactions or other injury resulting from participation in this research study.

In the event of a severe allergic reaction, the CTC is staffed with trained medical personnel and stocked with appropriate medical emergency equipment to provide acute care for conditions such as anaphylaxis. Further, if required, a formal emergency medical response service (fire department), capable of treating and transferring any life-threatening injuries to a higher level of medical care, is available in close proximity to the trial site.

5.2.1. 7-Day Solicited Reactogenicity and Follow-up

Temperature and solicited local and systemic signs/symptoms will be recorded in the clinic prior to vaccination and at a minimum of 30 minutes post injection and then daily by the participant for 7 days. Solicited symptoms that persist after the end of day 7 will be considered an AE/SAE and will be reported (see section 7.5) and followed through resolution.

Participants will be given a “Diary Card”, a thermometer, and a ruler. The diary card will be used as a memory aid, on which the participant will record temperature, local and systemic symptoms and concomitant medications daily for 7 days after the injection. Participants will be trained to complete the paper diary card, how to use the thermometer, and how to measure injection site swelling and redness using the ruler. Completion of the diary card training will be noted in source documents. The written (paper) diary card will be transcribed into the study database and will be stored in the participant file for monitoring purposes.

The solicited signs and symptoms on the diary card (among others) will include: joint pain, unusually tired, muscles aches (other than at injection site), headache, chills, nausea, and pain at injection site. Participants will also record the day’s highest measured temperature and measurement of largest diameter for redness and swelling at the injection site. The completed diary cards are collected at the first visit following completion of the 7-day diary card (about 2 weeks after the injection).

Follow-up on participant well-being will be performed by telephone or clinic visit on the day following vaccination and by clinic visit on Day 3 following the injection to assess their clinical status. Participants may call or come to the clinic at any time-point for evaluation, if they experience unusual, moderate or severe signs and symptoms. Diary cards will be reviewed with the clinician at any visit from day of vaccination through the first study visit following completion of the diary card. If upon reviewing the clinician finds that general symptom or injection site symptom information (except swelling or redness measurements) is missing from the diary cards, the participant will be asked to provide the missing information to the best of their recollection.

At every visit through study day 28, all participants will be asked about other interim adverse experiences, which will be recorded in source documents and entered into the study database within 3 business days. After study day 28, only serious adverse events and new chronic medical conditions that require ongoing medical management will be recorded in source documents and entered into the database, through the last study visit. All other adverse events will be recorded on source documents only. The PI or designee will assess the relationship of the study product to the events.

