3.0 ENDPOINTS

3.1. Primary Endpoints: Safety

Assessment of product safety will include clinical observation and monitoring of clinical chemistry and hematology parameters. Safety will be closely monitored after injection and evaluated through 48 weeks after the study injection. The following parameters will be assessed for all study groups:

- Occurrence of solicited local reactogenicity signs and symptoms for 7 days following the vaccination
- Occurrence of solicited systemic reactogenicity signs and symptoms for 7 days following the vaccination
- Change from baseline for safety laboratory measures
- Occurrence of adverse events of all severities through 28 days after the study injection
- Occurrence of serious adverse events and new chronic medical conditions through the last study visit

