7.0 PHARMACOVIGILANCE, SAFETY AND ADVERSE EVENT REPORTING

7.1. Definitions

Adverse Events

An adverse event (AE) is any untoward or unfavorable medical occurrence in a participant administered a pharmaceutical product and does not necessarily have a causal relationship with this product. An AE can therefore be any unfavorable and unintended sign (including an abnormal laboratory finding), symptom, or disease temporally associated with the use of a study product, whether or not considered related to the study product. (International Conference on Harmonization (ICH) E6) (Synonym: Adverse Experience).

Serious Adverse Events

As defined in 21 CFR 312.32, an adverse event or suspected adverse reaction is considered "serious" if, in the view of either the investigator or sponsor, it results in any of the following outcomes: "Death, a life-threatening adverse event, inpatient hospitalization or prolongation of existing hospitalization, a persistent or significant incapacity or substantial disruption of the ability to conduct normal life functions, or a congenital anomaly/birth defect. Important medical events that may not result in death, be life-threatening, or require hospitalization may be considered serious when, based upon appropriate medical judgment, they may jeopardize the participant and may require medical or surgical intervention to prevent one of the outcomes listed in this definition. Examples of such medical events include allergic bronchospasm requiring intensive treatment in an emergency room or at home, blood dyscrasias or convulsions that do not result in inpatient hospitalization, or the development of drug dependency or drug abuse."

"Life-threatening" refers to an adverse event that at occurrence represents an immediate risk of death to the participant; it does not refer to an event that hypothetically might have caused death if it were more severe. Similarly, a hospital admission for an elective procedure is not considered an SAE.

All AEs will have their possible relationship to study vaccine assessed and will be graded according to the table for grading severity of adverse events (see Appendix 9). Arthralgia (joint pain) and arthritis AEs will be graded in accordance with the criteria in Appendix 10.

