7.2. Adverse Event Grading and Recording

Recording of all AEs will occur during the period from study agent administration through 28 days after study agent administration. Solicited AEs will be recorded in the study database for 7 days after injection without the collection of attribution to study vaccine. All unsolicited AEs and SAEs that occur during the period from study agent administration through 28 days after study agent administration will be recorded in the study database. After study day 28, only SAEs and new chronic medical conditions that require ongoing medical management will be recorded as AEs in the study database. Because this is a Marburg vaccine study, in the extremely unlikely circumstance of Marburg diagnosis in a study participant at any time throughout the study, this will be recorded on a "Marburg CRF", rather than an AE form, without requiring an investigator attribution ("relatedness to study agent") or severity grade.

The FDA Guidance for Industry (September 2007): "Toxicity Grading Scale for Healthy Adult and Adolescent Volunteers Enrolled in Preventive Vaccine Clinical Trials" was adapted for the severity grading of adverse events in this protocol. The FDA Guidance of Industry on toxicity

grading scale is modified for criteria on absolute neutrophil counts and other parameters as described in Appendix 9, which also includes the definitions for severity grading parameters that do not have specific guidelines in the table. Due to the absence of specific grading criteria for arthralgias on the FDA toxicity grading scale, the “DAIDS AE Grading Table Corrected” (Version 2.1-July 2017) (Appendix 10) will be used to grade arthralgia AEs.

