The clinical investigators will monitor and analyze study data including all AE and lab data as they become available and will make determinations regarding the severity of the adverse experiences and their relation to study product. AE CRFs will be completed by the research staff on a daily basis as the data become available from the clinic or laboratory. AEs are also subjected to analysis to identify those that may invoke study pause rules. Although post injection reactogenicity (PIR)/Solicited AEs are documented separately from unsolicited AEs, they will be reported if they meet SAE or study pause rule definitions as noted below. Therefore the PI or designee must review both PIR and AE CRFs to ensure prompt and complete identification of all events that require expedited reporting as SAEs, study pause rules or other serious and unexpected events.

AEs will be followed by the clinical research team until resolved, and stability or chronicity has been established and documented.

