7.4. Criteria for Study Pause or Termination

The Principal Investigator will closely monitor and analyze study data as they become available and will make determinations regarding the presence and severity of adverse events. The administration of study injections and new enrollments will be paused and the IND Sponsor will be promptly notified according to the following criteria:

- **One** (or more) participant experiences a **SAE** that is assessed as possibly, probably or definitely related to study agent, or
- **Two** (or more) participants experience the same **Grade 3 or 4** adverse event assessed as possibly, probably or definitely related to study agent.

Plan for Review of Pauses and Resuming Rules:

The study injections and enrollments would resume only if review of the adverse events that caused the pause resulted in a recommendation to permit further study injections and study enrollments. The reviews to make this decision will occur as follows:

Pauses for SAEs: The IND Sponsor and PSRT will conduct the review, consult with the FDA, if needed, and make the decision to resume, amend or close the study for any SAEs that meet the criteria for pausing the study. The FDA will be notified of any SAE pause review.

Pauses for Grade 3 or 4 AEs: The IND Sponsor and PSRT will conduct the review and make the decision to resume, amend or close the study for the Grade 3 or 4 events that meet the criteria for pausing the study. As part of the pause review, the reviewers will also advise on whether the study needs to be paused again for any subsequent Grade 3 or 4 event of the same type. The FDA will be notified of all Grade 3/4 pause reviews.

When indicated, safety data reports and changes in study status (study pauses) will be submitted to the IRB in accordance with Section 12.2 and institutional policy.

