8.3.4. Interim analyses

Safety Reviews: The PSRT will review safety data routinely throughout the study. The study will utilize both electronic database features and reviews by designated safety review personnel to identify in a timely manner if any of the safety pause rules of the study are met.

Immunogenicity Review: Periodic analyses of immunogenicity for each group may be performed during the study for the purpose of informing future vaccine-related decisions in a timely manner once there are at least 3 participants in the group with the 4 weeks post vaccination follow-up completed. The results will not influence the conduct of the trial in terms of early termination or later safety or immunogenicity endpoint assessments.

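### After Day 28 a related Grade 3 or 4 event that is neither serious nor a new chronic condition gets no AE record in the database, although the two-participant pause criterion still counts it

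*Combined protocol and SAP*

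**What the plan says.** **Recording.** Section 5.2.1 narrows the entries once Day 28 has passed: "only serious adverse events and new chronic medical conditions that require ongoing medical management will be recorded in source documents and entered into the database". This limit applies until a participant's final visit. For everything else it says: "All other adverse events will be recorded on source documents only". Section 7.2 gives the same rule: "After study day 28, only SAEs and new chronic medical conditions that require ongoing medical management will be recorded as AEs in the study database". Neither makes an exception for grade or relatedness.

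**Pause rule.** Under Section 7.4, injections and new enrollment stop when two or more participants have the same Grade 3 or 4 "adverse event assessed as possibly, probably or definitely related to study agent". This criterion does not require the event to be serious or chronic, and it states no time window.

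**Detection.** Section 8.3.4: "The study will utilize both electronic database features and reviews by designated safety review personnel to identify" whether a pause rule is met. Section 7.2 adds that "the PI or designee must review both PIR and AE CRFs to ensure prompt and complete identification" of events that need expedited reporting or trigger a pause.

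**Scope.** The AE definition in Section 7.1 covers unfavorable signs, "including an abnormal laboratory finding". The primary AE endpoint in Section 3.1 is "Occurrence of adverse events of all severities through 28 days after the study injection".

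**The concern.** The pause rule and the recording rule cover different sets of events. A non-serious, non-chronic, related Grade 3 or 4 event after Day 28 counts toward a pause but creates no AE form, and two of the plan's detection tools work from the database and the forms.

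The trial keeps looking for such events after Day 28. Appendix 1 schedules an interim history at every visit, creatinine and ALT at Week 8, and blood counts at Weeks 8 and 24 and, as the table reads, Week 48. Section 5.2.3 requires a prompt repeat of specified Grade 3 or 4 laboratory results without a Day 28 limit.

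Two things are at stake. While Group 2 is being dosed, matching the same event across two participants could depend on people comparing source notes. At the end of the trial, the AE tables in Section 8.3.2, built on extracted data (Section 9.3), could show no late related Grade 3 or 4 event although the site had graded one.

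**Working it through.** The plan states no figure on this point, so there is none to reproduce. The check has three parts.

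**1. Which events fall in the gap**

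| Late related event (after Day 28) | AE record in database? | Counts toward a pause? |
|---|---|---|
| Serious | Yes | Yes, one is enough |
| Grade 3–4, new chronic condition needing ongoing management | Yes | Yes, in two participants |
| Grade 3–4, neither serious nor chronic | No | Yes, in two participants |
| Grade 1–2, neither serious nor chronic | No | No |

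The gap is the third row. Most clinical Grade 4 definitions in Appendix 9 are hospitalization, which Section 7.1 makes serious. The row therefore holds mainly clinical Grade 3 events and Grade 3–4 laboratory abnormalities.

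**2. How far late follow-up overlaps with dosing**

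Inputs from Sections 4.0 and 7.3: 20 per group; the first 3 dosed one per day; at least 7 days before the other 17; at least 7 days after the last Group 1 dose before Group 2 starts. The documents give no accrual rate for the 17, so I assume *r* per week, with no lag for the review itself.

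- Group 1 doses fall on days 0, 1, 2 and then 9 + floor(7*i*/*r*), for *i* = 0 to 16.
- Group 2 starts on day (last Group 1 dose + 7) and repeats the pattern.
- A Group 1 participant is past Day 28 at the first Group 2 dose if dosed more than 28 days before it.

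| | 2 per week | 3 per week | 5 per week |
|---|---|---|---|
| Last Group 1 dose | 9 + 56 = day 65 | 9 + 37 = day 46 | 9 + 22 = day 31 |
| First Group 2 dose | day 72 | day 53 | day 38 |
| Counted if dosed before | day 44 | day 25 | day 10 |
| Group 1 past Day 28 | 3 + 10 = **13** | 3 + 7 = **10** | 3 + 1 = **4** |
| Group 2 doses given with all 20 of Group 1 past Day 28 | 13 | 11 | 7 |
| Last Group 2 dose | day 137 | day 99 | day 69 |
| Group 1 at or past Week 8 by then | 20 | 18 | 7 |
| Group 2 past Day 28 by then | 11 | 7 | 3 |

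At all three rates, every Group 2 dose is given with at least two Group 1 participants past Day 28.

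Sensitivity: at one per day, 3 of 20 are past Day 28 at the first Group 2 dose. At one per week it is 16. If all 17 were dosed on a single day with no lag, Group 2 would be dosed on days 16 to 25 and the overlap would be nil. Review lags of 3 or 7 days increase the overlap.

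**3. Which safety-laboratory visit matters**

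The rule acts only while injections continue. Week 16 has no blood count, creatinine or ALT. The earliest possible Week 24 visit is 168 − 14 = day 154, after the last Group 2 dose at all three rates (days 137, 99 and 69). Week 8 is then the only post-Day-28 safety-laboratory visit within dosing. This depends on pace: at one per week the last dose is on day 249, and at two per week with a 7-day lag it is on day 158, so a Week 24 visit could also fall within dosing.

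**The case against.** The strongest reply is that the recording rule is deliberate and consistent, and that people, not the database, are the main safeguard. Much of that stands.

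- **Late events are not invisible.** Section 7.1 has every AE graded and assessed for relationship, with no Day 28 limit, and Section 5.2.1 assigns the relationship assessment to the investigator. Section 4.0 has a clinician review new safety data daily. Section 7.3 has the safety review team review all AEs, with weekly aggregate reports until 4 weeks after the last vaccination, which spans the whole dosing period. Appendix 12 has all AEs reported to the IND Medical Officer. A reader might infer that late severe events go ungraded or undetected; the documents do not support that.
- **Laboratory values are not lost.** Section 8.3.2 plots values measured throughout the study and tabulates changes from baseline, so the plan implies they are captured. Only the graded, attributed AE record is missing.
- **Most of follow-up is irrelevant to the pause rule.** Days 29 to 336 are 308 of 336 days (92%), but the rule acts only during dosing. On the calendar above, about 14%, 8% or 4% of post-Day-28 person-days fall before the last Group 2 dose.
- **Section 5.3 is not a clear contradiction.** It updates concomitant medication for related AEs after the first 7 days, which can be read as Days 8 to 28.
- **Section 3.1 is not contradicted.** It evaluates safety through 48 weeks but limits all-severity AEs to 28 days.

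The reply does not close the mismatch. Section 8.3.4 names database features as one of two routes, and Section 7.2 names form review as the means of complete identification. For these events neither has a record to work on.

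**Conclusion.** The point holds in a narrow form. The recording rule leaves out a class of event that the pause criterion counts: related, Grade 3 or 4, after Day 28, neither serious nor a new chronic condition. Such events would be absent from the automated pause check, from the Section 8.3.2 AE tables, and from the safety team's aggregate reports so far as these are drawn from the database, which is likely but not stated. The 28-day primary AE endpoint is unaffected.

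The number of participants exposed to the gap while dosing continues depends on accrual, which is an assumption here: about 13, 10 or 4 of 20 in Group 1 at the first Group 2 dose for 2, 3 or 5 per week, plus early Group 2 participants later on. It vanishes only at an implausibly fast pace.

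The documents give no rate for such late events. If the true risk of one particular event were 1%, 2%, 5% or 10%, the chance of at least two cases among 20, 1 − (1 − *p*)^20 − 20*p*(1 − *p*)^19, would be 1.7%, 6.0%, 26.4% or 60.8%. These figures take all 20 as fully observed, so they are upper bounds for events that arise while dosing continues. This is a cheap improvement to data capture, not a failure of safety oversight.

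**What to change.** Reconcile Sections 5.2.1 and 7.2 (recording) with Sections 7.2 (form review), 7.3, 7.4 and 8.3.4:

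- In Sections 5.2.1 and 7.2, add to the post-Day-28 database entries, through the last visit, any AE or laboratory abnormality that is both Grade 3 or higher and assessed as possibly, probably or definitely related. Use the AE form, with grade and attribution.
- In Section 8.3.2, add a line tabulating these events separately from the Day 0–28 all-severity endpoint, which stays as it is.

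All other late non-serious, non-chronic events stay in source only. The pause criterion, including whether it should have a time window, is left to the sponsor.

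The cost is protocol wording and probably a few extra AE forms in 40 participants, using information already held in source. The downside is slightly more data entry and coding.
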